Clinical Efficacy Analysis of Resveratrol in the Treatment of Primary Ovarian Insufficiency

Date: May 16, 2022

Research Proposal Summary

Scheme number	LCYJ-B05
Scheme name	Clinical effect of resveratrol on early onset ovarian insufficiency
Version number/date	Version 2.1, May 16, 2022
Indications	POI
Test purpose	In order to evaluate the role of resveratrol in the occurrence and development of a variety of ROS-related diseases including POI/POF, and to clarify the clinical effect and mechanism of resveratrol antioxidant therapy.
Research design	Prospective, multicenter, randomized, controlled clinical trial design
Total number of cases	150
Number of research centers	4
Study period	36 months
Research object	Diagnostic criteria : The diagnostic criteria for premature ovarian insufficiency (POI) refer to the “2017 Chinese Expert Consensus on Clinical Diagnosis and Treatment of Premature Ovarian Insufficiency” and “2016 Expert Consensus on Hormone Supplementation Therapy for Premature Ovarian

Insufficiency”; including: (1) Age <40 years old; (2) oligomenorrhea or amenorrhea for at least 4 months; (3) at least 2 times serum basal follicle-stimulating hormone (FSH) >25IU/L (interval > 4 weeks). Subclinical POI: FSH level is 15~25 IU/L, which is a high-risk group.

The diagnostic criteria for premature ovarian failure (POF) refer to the “2017 Chinese Expert Consensus on Clinical Diagnosis and Treatment of Premature Ovarian Insufficiency”, which refers to amenorrhea, FSH>40IU/L, and decreased estrogen levels before the age of 40, accompanied by varying degrees of perimenopause Stage symptoms are the terminal stage of POI.

standard constrain:

1. Amenorrhea or oligomenorrhea at least 4 months and two (>4 weeks interval) basal FSH \geq 10mIU/ml;
2. age<40 years old;
3. Informed consent, voluntary experiment.

Exclusion criteria:

1. Pregnant and lactating patients;
2. Patients with endometriosis, adenomyosis, endometrial lesions (submucosal fibroids ,endometrial polyps, etc.) , uterine fibroids>4 cm or hysterectomy;
3. Patients with adrenal cortical hyperplasia or tumor;
4. Ovarian neoplasms patients;
5. Hydrosalpinx patients;
6. Hyperprolactinemia patients;
7. Patients who are participating in other clinical trials or

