	
have participated in other clinical trials within the past three months;
 
8. Patients with suspected or real history of alcohol and drug abuse;
 
9. Known allergy to the investigational drug or its components;
 
10. Other patients deemed unsuitable for participation in this trial by the investigator.
 
Note: Patients who were receiving hormone replacement therapy at the time of recruitment were required to take at least a 3-month suspension of medication to participate in this trial.

Trial grouping and medication
	
1. POI patients group: According to the computer-generated random sequence, eligible patients were randomly assigned to the RES group and non-RES group according to 1: 1. POI IVF patients were divided into two groups: the RES treatment group (group A) and the non-RES treatment group (group B). Basal sex hormone and anti-Muller tube hormone were administered on day 2/3 of the menstrual cycle before treatment and 3 months after treatment. Antral Follicle (AFC) was detected by transvaginal B-ultrasonography, and basic sex hormones included follicle-stimulating hormone (FSH), Luteinizing hormone (LH), Estradiol 2 (E₂) and Testosterone (T).
 
2. Medication: Patients in group A received oral RES at 250mg daily for three months, and those in the non-RES group received oral vitamin E at 100mg daily for three months.

Treatment and follow-up
	
Course of treatment: Patients in group A received oral RES at 250mg daily for three months, and those in the non-RES group received oral vitamin E at 100mg daily for three months. All patients used microstimulation to superstimulate ovulation, and

clomiphene 50-150mg was taken orally from the 3rd to 5th day of menstruation, once a day for a total of 5 days later, the sex hormones and follicular diameter were checked, and 150-300IU Gonadotropin (Gn) was added as appropriate to the night needle day. After follicle maturation, 10000IU of Human Chorionic Gonadotropin (HCG) was injected intramuscularly or 250ug Ovidrel subcutaneously to induce ovulation. 36-38 hours later, a vaginal ultrasound-guided puncture was performed to collect eggs.

Specific inspection items include:

1. The patient's hormone levels (basal FSH, LH, E2, T) were detected on day 2/3 of the menstrual cycle;
2. Anti-Mullerian hormone (AMH) was detected in patients on day 2/3 of the menstrual cycle;
3. The numbers of antral follicles (AFC) were recorded by B ultrasound transvaginal;

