4. Pregnancy was recorded at the outpatient follow-up for patients with reproductive needs ;
5. Patients were routinely tested for blood routine (RBC, WBC, PLT, HGB), liver function (ALT, AST) and renal function (BUN, Cr), and recorded adverse events.

Note:

1. Basal follicle-stimulating hormone (FSH) $\geq 10\text{mIU/ml}$ at the first visit, and if other inclusion criteria are met if the patient has a history of testing with a baseline FSH $\geq 10\text{mIU/ml}$ in the past (interval > 4 weeks), he or she can be included in this study and drug therapy can be started; (Interval > 4 weeks) If the basic FSH $\geq 10\text{mIU/ml}$ has not been diagnosed, the patient is required to visit the hospital again after 4 weeks. If the basic FSH is still $\geq 10\text{mIU/ml}$, they can be included in this study and drug therapy

	
can be started.
 
2. For patients with regular menstrual periods, the basal FSH and antral follicle count (AFC) should be followed up on the 2nd to 4th day of the menstrual cycle. If the patient has menstrual cramps after the follow-up and has not exceeded the visit window, they are required to re-examine on the 2nd to 4th day of the menstrual cycle and record the examination data.

Study endpoint	
Primary endpoint : FSH, LH
 
Secondary endpoints :
 
(1) FSH, LH, E₂, T; (2) Antral follicle count (AFC); (3) Basal sex hormones and Anti- Mullerian hormone (AMH) on day 2/3 of the menstrual cycle; (4) Embryo laboratory indicators including number of eggs harvested, number of MII eggs, normally fertilized number, and number of good quality embryos; (5) Peripheral blood human villous gonadotropin (HCG); (6) Clinical pregnancy rate (patients with reproductive needs).

Security indicators	
1. Blood routine (RBC, WBC, PLT, HGB) , liver function (ALT, AST) and renal function (BUN, Cr) ;
 
2. Patient adverse events were recorded.

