Clinical Efficacy Analysis of Resveratrol in the Treatment of Primary Ovarian Insufficiency

Date: May 16, 2022

Research Proposal Summary

Statistical analysis

The case observation form completed by the test center was reviewed and returned by the project team of Reproductive Medicine Center, Affiliated Hospital of Nantong University, and the data was processed by a statistical analyst. The data in the case report form is entered in two copies, and the database is locked after verification and confirmation. SPSS26.0 software was used for statistical analysis. The full analysis set (FAS) and the per-protocol set (PPS) were used for effectiveness analysis, and the safety data set (SS) was used for safety analysis. Measurement data were expressed as mean±standard deviation ($\bar{x}\pm s$), multiple time points were compared by repeated measures analysis of variance, and pairwise comparisons were by Bonferroni test; enumeration data were expressed by the number of cases or percentages, and χ^2 was used. Test for statistical comparison. $P<0.05$ indicated that the difference was statistically significant.

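### FSH is both the entry variable and a primary endpoint, and the qualifying reading can serve as baseline, so the SAP's time-point tests can show a fall without any drug effect; the SAP does not name the unbiased between-arm contrast as the efficacy test

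*Protocol*

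**What the plan says.** - **Entry** (protocol, Research object, first inclusion criterion): "Amenorrhea or oligomenorrhea at least 4 months and two (>4 weeks interval) basal FSH", each at or above 10 mIU/ml.
- **Endpoint** (protocol, Study endpoint): "Primary endpoint : FSH, LH".
- **Start of treatment** (protocol, Note 1 after the inspection items): a woman with a qualifying first-visit FSH and a past qualifying value may start at once: "he or she can be included in this study and drug therapy can be started". A woman with no past value returns after 4 weeks, and a qualifying repeat has the same consequence. The past value has a minimum interval but no maximum age.
- **Measurement times** (protocol, Trial grouping and medication): hormones are taken "on day 2/3 of the menstrual cycle before treatment and 3 months after treatment". The pre-treatment sample is not required to be separate from the qualifying one, and no baseline is defined.
- **Analysis** (SAP, Statistical analysis): for measurement data, "multiple time points were compared by repeated measures analysis of variance, and pairwise comparisons were by Bonferroni test", at a 0.05 significance level. No group-by-time term, baseline adjustment or between-arm contrast is named for these data.
- **Allocation** (protocol, Trial grouping and medication): randomised 1:1 between resveratrol and a concurrent vitamin E arm; 150 women in total.

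**The concern.** A reading accepted only because it reached a threshold contains, on average, some upward chance deviation. The next reading does not carry that deviation, so its mean is lower even if nothing has changed. Here the variable used for selection is also a primary endpoint, and the selected reading can be the before-treatment value.

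The distortion falls on change over time: within each arm, and in the time effect over both arms. Those are the comparisons that the SAP's wording most directly describes. A significant fall in the resveratrol arm, or in both arms, would meet the SAP's written criterion for significance. It could then be read as benefit when it came from the entry rule.

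**Working it through.** The plan gives no figure for this effect, so there is nothing to reproduce. From the documents come the threshold of 10 mIU/ml on two readings, one measurement before treatment and one at 3 months, significance at 0.05 (taken as two-sided), and 150/2 = 75 per arm. The FSH distribution and its variation within a woman are **assumed**.

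**Model.** For woman i at reading j, log FSH = m_i + e_ij. Here m_i is normal around the log of the screened median with SD s_b, and e_ij is independent noise with SD s_w. The test-retest correlation is r = s_b²/(s_b² + s_w²). A woman enters if readings 1 and 2 are both at least 10. Reading 2 is the baseline and reading 3 the 3-month value. There is no drug effect and no time trend.

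**Direction.** Among women who enter, e_i2 has a positive mean because reading 2 had to pass the threshold, while e_i3 has mean zero. The expected change in log FSH is therefore minus the mean of e_i2, which is below zero and the same in both arms.

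**Tests.**
- One arm: t = mean(D)/(s_D/√75), where D is the 3-month value minus baseline. A false fall has a nominal rate of 2.5%. With two time points there is one pair per arm, so a Bonferroni correction within an arm changes nothing.
- Between arms: t = (mean D_A − mean D_B)/√(s²_A/75 + s²_B/75), which corresponds to the group-by-time term. The nominal rate is 5%, two-sided.

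**Result 1: total log-SD 0.6, r from 0.5 to 0.85, raw scale.**

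| Screened median (mIU/ml) | False significant fall in one arm |
|---|---|
| 12 | about 7-24% |
| 20 | 3-6% |
| 30 | about 3% |

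Mean FSH falls by 0.6-8.5% over medians 12 to 20, and by 0.2-0.8% at median 30. On the log scale the false-fall rate over medians 12 to 20 is 6-58%.

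**Result 2: a second variance model.** Here s_b = 0.5 and s_w = 0.2, 0.3 or 0.4. The implied r runs from 0.25/(0.25 + 0.04) = 0.86 down to 0.25/(0.25 + 0.16) = 0.61.

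| Screened median | One arm, raw | One arm, log | Time main effect (fall), raw |
|---|---|---|---|
| 8 | 16-43% | 32-84% | 28-70% |
| 12 | 7-17% | 13-45% | 10-27% |
| 20 | 3-5% | 5-12% | 3-7% |
| 30 | 2-3% | 3-5% | about 3% |

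As an example, at median 12 and s_w = 0.4 the mean baseline is 21.15 and the mean 3-month value 19.82. The fall is 21.15 − 19.82 = 1.33 mIU/ml, and 1.33/21.15 = 6.3%.

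**Result 3: the between-arm test.** In the same scenarios, with the qualifying value kept as baseline, the false-positive rate was 4.6-5.6% (raw) and 4.7-5.3% (log) against a nominal 5%.

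**Result 4: a separate baseline.** With a reading drawn after qualification as baseline, the expected fall is zero and the one-arm rate is 2.2-3.0%. This confirms that the excess comes from reusing the selected reading.

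**The case against.** The strongest reply is that the trial is randomised with a concurrent control, so selection acts equally on both arms and cancels in the treatment comparison. That stands in full, and Result 3 shows it. A reader might infer that the estimate of treatment effect is biased; the documents do not support that.

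Second, a repeated measures ANOVA in a two-arm trial can include a group-by-time term, and the SAP nowhere says that a fall within an arm counts as efficacy. This also stands. A reader might infer that the plan makes such a claim, but it does not. What remains is that the SAP names comparisons over time and leaves the between-arm contrast unnamed. The regression problem is a consequence of that gap and would largely disappear once the contrast is specified.

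Third, the size is uncertain. The protocol's own diagnostic cut-off for POI is FSH above 25 IU/L. If most women screened are at that level the effect is small: at median 25, under the assumptions of Result 1, a false fall occurs in 2.9-4.0% of trials. Against this, the entry threshold of 10 lies below both that cut-off and the subclinical range of 15 to 25 IU/L, so women near the threshold are eligible. The documents do not say how many there will be.

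Fourth, a site may draw a separate pre-treatment sample. Note 1 permits reuse of the qualifying reading but does not require it.

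**Conclusion.** The point holds as a gap in the SAP, not as a bias in the randomised comparison. The entry rule, Note 1 and the choice of endpoint together allow a selected reading to be the baseline, and the stated time-point tests can then be significant with no drug effect.

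The size cannot be fixed from the documents. Under the assumptions of Result 1, the effect is material if many screened women are near 10 mIU/ml and negligible if most are well above it. The figure of 24% belongs to one unfavourable corner (median 12, r = 0.5) and should not be quoted alone. Analysis on the log scale or a lower screened median would raise it; a true rise in FSH over 3 months would offset part of the fall. The calculation concerns FSH only, since LH is not an entry variable.

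A reader might also infer that averaging the two qualifying values would cure the problem. It would not: both were selected to be at least 10, so their mean falls by essentially the same amount. Nor is a gain in precision assured. The residual variance ratio relative to a single baseline is 0.80-0.94 if the past value is as informative as the current one. It is about 1.08, a loss, at r = 0.85 if an old or outside-laboratory value carries an assumed extra log-SD of 0.4. Averaging also offers nothing for LH, for which no second value is required.

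**What to change.** Add to the SAP:

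1. The efficacy test for FSH and for LH is the between-arm difference at 3 months adjusted for the pre-treatment value, by ANCOVA or as the group-by-time term of the repeated measures ANOVA. State which of the two is used.
2. Within-arm changes from before to after treatment, and the main effect of time, are descriptive only and support no efficacy claim, because entry is conditional on high FSH.
3. A definition of which sample is the baseline, applied identically in both arms, including whether the qualifying reading may be used.

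Do not average the two qualifying values.

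The cost is a few sentences of SAP text, with no change to visits, eligibility or treatment. The downside is the loss of within-arm P values, which could not have supported an efficacy claim under this entry rule.

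### FSH and LH are both primary, but no rule says whether one or both must be significant; if either is enough, the false-positive chance exceeds 5%

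*Protocol*

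**What the plan says.** The Study endpoint row of the protocol gives "Primary endpoint : FSH, LH". It adds no conjunction, order or time point. Both hormones appear again in the first item of the secondary list.

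The SAP's Statistical analysis section is one paragraph. Three statements bear on this point:

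- For measurement data, "multiple time points were compared by repeated measures analysis of variance, and pairwise comparisons were by Bonferroni test".
- A single threshold applies throughout: P<0.05 "indicated that the difference was statistically significant".
- Two populations are named for efficacy, with neither marked as primary: "The full analysis set (FAS) and the per-protocol set (PPS) were used for effectiveness analysis".

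Under Trial grouping and medication, the protocol has basal sex hormones taken "on day 2/3 of the menstrual cycle before treatment and 3 months after treatment", which gives one pre-treatment and one later value per patient. Neither document states a rule across the two hormones, the sidedness of the tests, an assumed FSH–LH correlation, or a derivation of the total of 150.

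**The concern.** With two primary variables, each judged at 0.05, a reader cannot tell what result makes the trial positive. One reading (either hormone) lets the error of the primary claim rise above 5%. The other (both hormones) does not. With no rule fixed in advance, the choice of reading can follow the results.

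A second gap sits underneath. Any rule across two hormones needs one p-value from each. A repeated-measures ANOVA gives three: group, time and group-by-time. The time effect pools the arms and says nothing about resveratrol against vitamin E. The group effect averages in the pre-treatment value. The SAP does not say which term decides, or in which analysis set.

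**Working it through.** **Inputs.** Two primary variables (protocol, Study endpoint). Threshold 0.05 per test (SAP). 150 patients randomised 1:1, so 75 per arm (protocol). Assumed, because the documents are silent: two-sided tests, one test per hormone, and a correlation r between the two test statistics. The plan states no overall error rate or power, so there is no figure of its own to reproduce.

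**Step 1: either hormone suffices, neither truly differs.** The chance of at least one false positive is 1 − P(|Z1| < 1.96 and |Z2| < 1.96), with Z1 and Z2 bivariate normal with correlation r. At r = 0 this is 1 − 0.95² = 0.0975.

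**Step 2: both required, neither truly differs.** The chance is 0.05 + 0.05 minus the Step 1 figure. At r = 0 this is 0.10 − 0.0975 = 0.0025. If one hormone truly differs, a false joint claim still needs the other to be significant at 0.05, so the error stays at or below 5%.

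**Step 3: Holm.** When neither differs, an error requires at least one p-value below 0.025. At r = 0 this is 1 − 0.975² = 0.0494.

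| r (assumed) | Either suffices | Both required | Holm |
|---|---|---|---|
| 0 | 9.75% | 0.25% | 4.9% |
| 0.5 | 9.1% | 0.93% | 4.6% |
| 0.8 | 7.8% | 2.2% | 4.0% |
| 0.9 | 7.0% | 3.0% | 3.6% |
| 0.95 | 6.5% | 3.5% | 3.3% |

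Simulated two-sample t-tests with 75 per arm agree with the second column: 9.5% at r = 0, 9.0% at 0.5, 7.9% at 0.8 and 7.1% at 0.9.

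**Step 4: what each rule costs in power.** The documents give no effect or SD. As an illustration, assume an unadjusted two-sample t-test, no dropout and an effect of 0.46 SD, chosen because it gives 80% power at 0.05 with 75 per arm.

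- Fixed sequence, FSH first: FSH keeps 80%. If both hormones respond, LH can be claimed 64% of the time at r = 0 (0.80 × 0.80) and 75% at r = 0.9. If LH alone responds, it can be claimed 4% of the time at r = 0 (0.05 × 0.80) and 2.5% at r = 0.9.
- Holm: power at the first step, 0.025, is about 71%.
- Both required: joint power is 64% at r = 0, 70% at 0.6 and 75% at 0.9.

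**Step 5: effect of baseline adjustment.** If the pre/post correlation is 0.5 (assumed), adjustment multiplies the residual variance by 1 − 0.5² = 0.75. The effect becomes 0.46/√0.75 = 0.53 residual SD. Power is then about 90% at 0.05 and 84% at 0.025.

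The group-by-time term with two time points is a t-test on change, whose variance is 2(1 − 0.5) = 1.0 times that of a single value. At that correlation it gains nothing over the unadjusted comparison.

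**The case against.** The strongest reply is that the inflation is conditional. The protocol's heading for this line is singular, while the secondary heading is plural, which could point to one joint endpoint. If so, no error is inflated. This stands as far as it goes: a reader might infer that the trial runs at up to 9.75% error, and the documents do not establish that. Nor do they establish the joint reading, because a singular heading in a translated summary is thin evidence.

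A second reply is that the SAP already uses Bonferroni. It does, but that step is tied to pairwise comparisons alongside the comparison of time points. Nothing extends it to two hormones.

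A third reply is that the planned ANOVA need not be replaced. That is right. With one pre- and one post-treatment value, the group-by-time term gives one between-group p-value per hormone, and naming it would meet the minimum need. Baseline adjustment is a preference, on grounds of precision.

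A reader might also infer that requiring both hormones costs nothing and that only Holm would call for more patients. Under the Step 4 assumptions, 80% power takes about 91 per arm at Holm's first step, and 80% joint power takes about 98, 92 or 84 per arm at correlation 0, 0.6 or 0.9. Both rules lower power at 150 patients.

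Finally, the hormone timing "on day 2/3 of the menstrual cycle before treatment and 3 months after treatment" could mean the end of the three-month dosing or three months after it. That is a separate question about endpoint timing. It creates no multiplicity and should be raised on its own.

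**Conclusion.** The point holds as a missing decision rule. Two primary hormones are tested at 0.05, and nothing says what counts as success. The either-hormone error of 6.5% to 9.75% rests on that reading, two-sided testing, one test per hormone, and an assumed correlation from 0.95 down to 0. It does not count the further choice among ANOVA terms or between the two analysis sets. Under the both-hormones reading, error does not exceed 5%.

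Because the inflation depends on the reading, this is a defect to settle before the data are compared by group. It does not show that the trial's error rate is already wrong. The repeat of FSH and LH among the secondary endpoints is untidy but does not change the primary error.

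**What to change.** Before database lock and before any comparison by group:

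1. State one primary rule that holds overall error at 0.05. A fixed sequence suits this protocol: FSH first, since the protocol uses it to define POI and eligibility ("Amenorrhea or oligomenorrhea at least 4 months and two (>4 weeks interval) basal FSH", with a threshold), then LH at 0.05 only if FSH is significant. Holm across the two hormones, or requiring both at 0.05, also controls the error.
2. Name one between-group test per hormone. Preferably, compare the post-treatment basal value adjusted for the pre-treatment value already collected. The group-by-time term of the planned ANOVA is an acceptable minimum.
3. State that the full analysis set carries the primary conclusion and the per-protocol set is supportive.
4. Remove FSH and LH from the secondary list as a tidy-up.

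The cost is a line in the endpoint table and two or three SAP sentences. No extra patients are proposed. The price lies in power. Under the fixed sequence FSH keeps its full power, but LH can rarely be claimed if LH alone responds. Holm and both-required each lower power at 150 patients, by the illustrative amounts in Step 4. Baseline adjustment would recover some or all of that, depending on the pre/post correlation. If data have already been compared by group, the rule can no longer be called prespecified; the report should say so and give both hormones.
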